## SYNOPSIS

Protocol Title:	A Single-Center, Randomized, Double Masked, Placebo Controlled Clinical Study to Assess the Safety and Efficacy of Topical Naltrexone Ophthalmic Solution on the Signs and Symptoms of Dry Eye in Diabetic Subjects
Protocol Number:	DDES001
Investigational Product:	1) Naltrexone Ophthalmic Solution, 0.002% 2) Placebo Ophthalmic Solution
Study Phase:	2
Primary Objective(s):	The objective of this exploratory study is to determine the safety and efficacy of 0.002% Naltrexone Ophthalmic Solution, compared to placebo for the treatment of the signs and symptoms of dry eye in diabetic subjects.
Secondary Objective(s):	To assess the tolerability of twice daily administered 0.002% Naltrexone Ophthalmic Solution, eye drops vs placebo
Overall Study Design:	
Structure:	Single-center, double-masked, randomized, placebo-controlled study
Duration:	An individual subject's participation is estimated to be approximately 38 days
Controls:	Placebo (vehicle minus active) Ophthalmic Solution
Dosage/Dose Regimen/ Instillation/Application/Use:	Screening: During a 10-day study run-in period (for the purpose of subject selection) prior to randomization, all subjects will receive Placebo Ophthalmic Solution (Vehicle) bilaterally BID Subjects eligible to be randomized will receive one of the following treatments to be administered bilaterally BID for 29 days (from Visit 2 to Visit 5).

	1) Naltrexone Ophthalmic Solution, 0.002% 2) Placebo Ophthalmic Solution (Vehicle)
Summary of Visit Schedule:	5 visits over the course of approximately 6 weeks: 

• Visit 1 = Day <math>-10 \pm 1</math>, Screening

• Visit 2 = Day 1, Confirmation / Baseline

• Visit 3 = Day <math>8 \pm 1</math>, One Week Follow-Up

• Visit 4 = Day <math>15 \pm 1</math>, Two Week Follow-Up

• Visit 5 = Day <math>29 \pm 2</math>, Four Week Follow-Up and Study Exit

Measures Taken to Reduce Bias:	This is a randomized treatment assignment, double masked study.
Study Population Characteristics:	
Number of Subjects:	60 (30 per treatment arm) subjects
Condition/Disease:	Diabetic subjects with Dry Eye Syndrome

Inclusion Criteria:	
Subjects must:
 

a. Be at least 18 years of age;

b. Provide written informed consent;

c. Have a diagnosis of type 1 or type 2 diabetes mellitus prior to Visit 1;

d. Have a reported history of dry eye for at least 6 months prior to Visit 1;

e. Have a history of use or desire to use eye drops for dry eye symptoms within 6 months of Visit 1;

f. Have a corneal fluorescein staining score of <math>\geq</math> 2 in any region (inferior, superior, or central regions) in at least one eye at Visits 1 and 2 (must be the same eye at Visits 1 and 2);

g. Have at least one of the following at Visits 1 and 2:

1. A total lissamine green conjunctival score of <math>\geq</math> 2 in at least one eye, based on the sum of the temporal and nasal regions at Visits 1 and 2 (must be the same eye at Visits 1 and 2);

2. Report an OSDI score <math>\geq</math> 20 at Visits 1 and 2.

Exclusion Criteria:	
Subjects must not:
 

a. Have any clinically significant slit lamp findings at Visit 1 that may include active blepharitis, meibomian gland dysfunction (MGD), lid margin inflammation or active ocular allergies that require therapeutic treatment, and/or in the opinion of the investigator may interfere with study parameters;

b. Be diagnosed with an ongoing ocular infection (bacterial, viral, or fungal), or active ocular inflammation at Visit 1;

c. Have concurrent neurotrophic keratopathy from a source other than diabetes (h/o HSV keratitis, h/o HZO with ocular manifestations, or CN VII palsy or other condition resulting in lagophthalmos);

d. Have active diabetic foot ulcers;

	

e. Have a corneal sensitivity score <math>\leq</math> 1.5 cm as measured by Cochet-Bonnet at Visit 1;

f. Report an OSDI score <math>></math> 75 at Visits 1 and 2;

g. Have worn contact lenses within 21 days of Visit 1 or anticipate using contact lenses during the study (no contact lens wear during study);

h. Have used any eye drops within 2 hours of Visit 1;

i. Have previously had laser-assisted in situ keratomileusis (LASIK) surgery within the last 24 months;

j. Have used cyclosporine 0.05% or lifitigrast 5.0% ophthalmic solution within 45 days of Visit 1;

k. Have any planned ocular and/or lid surgeries over the study period or any ocular surgery within the last 12 months;

l. Be using or anticipate using temporary punctal plugs during the study that have not been stable within 30 days of Visit 1;

m. Be currently taking any topical ophthalmic prescription (including medications for glaucoma) or over-the-counter (OTC) solutions, artificial tears, gels or scrubs, and cannot discontinue these medications for the duration of the trial (excluding medications allowed for the conduct of the study);

n. Have corrected visual acuity greater than or equal to logMAR +0.7 as assessed by Early Treatment of Diabetic Retinopathy Study (ETDRS) scale in either eye at Visit 1;

o. Have concurrent autoimmune disease causing dry eye (e.g., rheumatoid arthritis, Sjogren's, GVHD, Steven's Johnson, Grave's);

p. Have Fuchs endothelial dystrophy;

q. Have recurrent corneal erosion syndrome or anterior basement membrane dystrophy;

r. Be a woman who is pregnant, nursing, or planning a pregnancy;

s. Be unwilling to submit a urine pregnancy test at Visit 1 and Visit 5 (or early termination visit) if of childbearing potential. Non-childbearing potential is defined as a woman

--	--

	
who is permanently sterilized (i.e., has had a hysterectomy or bilateral tubal ligation), or is post-menopausal (without menses for 12 consecutive months);
 

t. Be a woman of childbearing potential who is not using an acceptable means of birth control; acceptable methods of contraception include: hormonal – oral, implantable, injectable, or transdermal contraceptives; mechanical – spermicide in conjunction with a barrier such as a diaphragm or condom; IUD; or surgical sterilization of partner. For non-sexually active females, abstinence may be regarded as an adequate method of birth control; however, if the subject becomes sexually active during the study, they must agree to use adequate birth control as defined above for the remainder of the study;

u. Have a known allergy and/or sensitivity to the test article or its components;

v. Have a condition or be in a situation which the investigator feels may put the subject at significant risk, may confound the study results, or may interfere significantly with the subject's participation in the study;

w. Be currently enrolled in an investigational drug or device study or have used an investigational drug or device within 30 days of Visit 1;

x. Be currently using any medication known to cause ocular drying that is not used on a stable dosing regimen for at least 30 days prior to Visit 1;

y. Be unable or unwilling to follow instructions, including participation in all study assessments and visits.

z. Be currently using a systemic opioid antagonist (e.g., Naltrexone or Naloxone) or have used a systemic opioid antagonist in the previous 90 days

Study Formulations and Formulation Numbers:	

• Naltrexone Ophthalmic Solution, 0.002%

• Placebo Ophthalmic Solution

Efficacy Measures and Endpoints:	
Efficacy Measures:
 

• Fluorescein staining; regions: inferior, superior, central, corneal sum, temporal, nasal, conjunctival sum, total eye;

• Lissamine green staining; regions: inferior, superior, central, corneal sum, temporal, nasal, conjunctival sum, total eye;

• Tear film break-up time (TFBUT);

• Conjunctival redness;

• Schirmer's Test (without anesthesia);

• Cochet-Bonnet Corneal Sensitivity

• Tear Osmolarity;

• MMP-9;

• Total Ocular Surface Disease Index (OSDI);

• Ocular discomfort (0-4 scale);

• Ocular discomfort, dryness, grittiness, burning and stinging (0-5 scale);

• VAS.

Safety Measures:	

• Visual acuity;

• Slit-lamp biomicroscopy;

• Adverse event query;

• IOP;

• Dilated fundoscopy.

General Statistical Methods and Types of Analyses	
Analysis Populations	

• Modified Intent-to-Treat Population – The modified intent-to-treat (mITT) population includes all randomized subjects with at least one post visit 2 study assessment. Efficacy analysis will be performed on the mITT population. Subjects in the mITT population will be analyzed as randomized.

• Safety Population – The safety population includes all subjects who have received at least one dose of the investigational product. Subjects in the Safety population will be analyzed as treated.

 
The statistical analysis of safety data will be performed for the safety population. The analysis of baseline and all efficacy data will be performed for the mITT population.
 
Sample Size:
	

As an exploratory study, the study is not powered to show statistical differences for any of the efficacy endpoints.

With a sample size of 60 subjects in the Safety and Efficacy Assessment, the study will have 79% probability of detecting AEs occurring at a rate of 5% or more in either treatment arm.

**Multiplicity Consideration:**

There will be no adjustments for multiple endpoints or multiple treatment comparisons for this early phase, exploratory study.

**Safety Variables:**

Frequencies and percentages of subjects with treatment-emergent adverse events (TEAEs), serious TEAEs, and TEAEs causing premature discontinuation will be provided by treatment group. An AE is treatment emergent if it occurs or worsens after the first dose of study treatment. Separate summaries will be provided for ocular specific and all AEs (including systemic).

Other safety endpoints including visual acuity, slit-lamp biomicroscopy, corneal sensitivity, dilated fundoscopy, intraocular pressure will be summarized by treatment group and visit using descriptive statistics. Changes or shifts from baseline will also be summarized where appropriate. For assessments performed by eye, study eye and fellow eye may be summarized separately.

**Summary of Known and Potential Risks and Benefits to Human Subjects**

The previous human experience with topical naltrexone administered to the eyes of healthy volunteers and the nonclinical safety studies conducted have indicated that topical naltrexone appears to be well tolerated. Nevertheless, patients will be closely monitored for safety-related issues.

## LIST OF ABBREVIATIONS

AE	adverse event
BCVA	best-corrected visual acuity
BID	twice daily
CFR	Code of Federal Regulations
CRA	clinical research associate
CRF	case report form
CRO	contract research organization
DED	dry eye disease
ETDRS	Early Treatment Diabetic Retinopathy Study
FDA	Food and Drug Administration
GCP	Good Clinical Practice
GLP	Good Laboratory Practice
HIPAA	Health Insurance Portability and Accountability Act
IB	Investigator's brochure
ICF	informed consent form
ICH	International Conference on Harmonisation
IND	investigational new drug application
IOP	intraocular pressure
IP	investigational product
IRB	institutional review board
ITT	intent to treat
KCS	keratoconjunctivitis sicca
LASIK	laser in situ keratomileusis
logMAR	logarithm of the minimum angle of resolution
MedDRA	Medical Dictionary for Regulatory Activities
Mg	microgram
µL	microliter
Mm	millimeter

NDA	new drug application
NEI	National Eye Institute
OD	right eye
OS	left eye
OSDI	Ocular Surface Disease Index
OU	both eyes
SAE	serious adverse event
SD	standard deviation
SOP	standard operating procedure
TF	tear film
TFBUT	tear film break-up time
VA	visual acuity

## 1 INTRODUCTION

### 1.1 Dry Eye Disease (DED)

Dry Eye Disease (DED) is defined by the International Dry Eye Workshop (DEWS) as a multifactorial disease of the ocular surface characterized by a loss of homeostasis of the tear film, and accompanied by ocular symptoms, in which tear film instability and hyperosmolarity, ocular surface inflammation and damage, and neurosensory abnormalities play etiological roles (DEWS II Definition and Classification 2017). As many as 5 - 35% of patients visiting ophthalmic clinics report dry eye symptoms, making it one of the most common conditions seen by ophthalmic specialists (McCarty CA, *et al.* 1998; Lin PY, *et al.* 2003). Estimates range from 20 million people in the United States (US) being affected with mild to moderate dry eye, to a high of as many as one out of every five Americans. Prevalence is greater in females and the elderly. Schaumberg *et al.* reported prevalence rates ranging from 3.9% in men aged 50–54 years to 7.7% in those 80 years or older, while an increased rate from 5.7% in women younger than 50 years to 9.8% in women >75 years was observed (Schaumberg DA, *et al.* 2003). Prevalence is affected by geographical parameters and appears to be higher in Asian populations. Dry eye can be related to external factors, such as the low humidity of air conditioned offices, winter heating, a dusty or windy outdoor environment, prolonged computer use, or wearing contact lenses, as well as to internal factors, such as hormonal imbalance, autoimmune disease, the presence of many widely prescribed systemic medications, anatomical changes or trauma, and aging. Symptoms result in mildly decreased quality of life at a minimum, and with increasing severity, loss of function and productivity, pain, light sensitivity, and the misery that accompanies significantly impaired vision and decreased quality of life. With the aging population in the United States and other countries of the developed world, and with increasing computer use, DED is expected to continue to become more prevalent and finding a treatment is becoming more important (Schaumberg DA, *et al.* 2009).

## STUDY TREATMENT

Researchers at Pennsylvania State University/Hershey Medical Center have been exploring the role of the Opioid Growth Regulatory System (OGRS), which includes Opioid Growth Factor (OGF), and its receptor, OGFr, in the health and healing of the corneal epithelium for nearly 20 years. These studies included evaluating the impact of the OGRS on healthy corneal epithelium and the healing of wounded corneal epithelium utilizing cell and organ culture. Experiments have been performed in living animals. Additionally, cell and organ culture experiments were performed utilizing human eye bank corneas not suitable for transplantation. These studies have demonstrated the safety and efficacy of topically applied naltrexone in expediting the healing of corneal epithelial wounds in normal and diabetic rats. This research led to an investigational drug study entitled: “Topical Application of Naltrexone to the Ocular Surface of Healthy Volunteers: A Tolerability Study” (Liang et al., Volume 32 (2), 2016, pp 127-132; DOI: 10.1089/jop.2015.0070). It was concluded that topical naltrexone was well tolerated in healthy human subjects after 1 or 4 eye drops of naltrexone at dosages up to ~3.76 µg administered over a 24-h treatment period and observed for 1 week.

## 2 STUDY OBJECTIVES

The objective of this study is to compare the safety and efficacy of Naltrexone Ophthalmic Solution, 0.002% to placebo for the treatment of the signs and symptoms of dry eye in diabetic subjects.

## 3 CLINICAL HYPOTHESIS

The clinical hypotheses for this exploratory study is that Naltrexone Ophthalmic Solution has a beneficial effect compared to vehicle in improving the signs and symptoms of DED.

## 4 OVERALL STUDY DESIGN

This is a Phase 2, single-center, double-masked, randomized, placebo-controlled study to compare the safety and efficacy of Naltrexone Ophthalmic Solution, 0.002% to placebo for the treatment of the signs and symptoms of dry eye in diabetic subjects. Subjects eligible to be randomized will receive one of the following treatments to be administered bilaterally BID for 29 days (from Visit 2 to Visit 5): Naltrexone Ophthalmic Solution, 0.002% or Placebo Ophthalmic Solution (Vehicle). During a 10-day study run-in period (for the purpose of subject selection) prior to randomization, all subjects will receive Placebo Ophthalmic Solution (Vehicle) bilaterally BID. Participants who terminate early during the application period will be asked to complete safety assessments (if the participants agree) prior to study exit. Participants who are terminated early from the study will not be replaced. A chart illustrating the study's structure is below.

Visit 1 Day $-10 \pm 1$ day Screening	

• Informed consent/Health Information Portability and Accountability Act (HIPAA) consent

• Demographic data, medical/medication, and ocular history

• Urine Pregnancy Test (if applicable)

• Ocular Surface Disease Index (OSDI)

• Ora Calibra® Ocular Discomfort Scale

• Ora Calibra® Ocular Discomfort & 4-Symptom Questionnaire

• VAS

• Best Corrected Visual Acuity (BCVA)

• Slit lamp biomicroscopy

• Ora Calibra® Conjunctival redness;

• Corneal sensitivity (Cochet-Bonnet)

• TFBUT;

--	--

	

• Fluorescein staining (Ora Calibra® scale); regions: central, superior, inferior, temporal, nasal, corneal sum, conjunctival sum, and total eye score

• Lissamine green staining (Ora Calibra® scale); regions: inferior, superior, central, temporal, nasal, corneal sum, conjunctival sum, and total eye score)

• Review inclusion and exclusion criteria

• Run-in (vehicle) dose

• Dispense vehicle to all qualifying patients for BID dosing until Visit 2

• Dispense dosing diary

• Adverse Event Query

• Schedule Visit 2

	↓
	Approximate 10-Day Run-In Period with Vehicle
Visit 2 Day 1 Confirmation/Baseline	↓ 

• Run-in and diary collection

• Medical/medication update

• Adverse event query

• Ocular Surface Disease Index (OSDI)

• Ora Calibra® Ocular Discomfort Scale

• Ora Calibra® Ocular Discomfort & 4-Symptom Questionnaire

• VAS

• BCVA

• Slit lamp biomicroscopy

• Ora Calibra® Conjunctival redness

• Corneal Sensitivity (Cochet-Bonnet)

• Tear Osmolarity

• InflammaDry® (MMP-9) testing

• Tear film break-up time (TFBUT)

• Corneal and conjunctival fluorescein staining

	

• Corneal and conjunctival lissamine green staining

• Unanesthetized Schirmer's Test

• Intraocular Pressure (IOP)

• Dilated fundoscopy

• Review inclusion and exclusion criteria

• Randomize qualifying subjects

• Study treatment dose

• Dispense study drug/placebo for BID dosing with active or placebo until Visit 5 according to randomization

• Dispense dosing diary

• Adverse Event Query

• Schedule Visit 3

	↓

Visit 3 Day 8 ± 1 day 1-Week Follow-Up
	

• Study drug and diary collection

• Medical/medication update

• Adverse event query

• OSDI

• Ora Calibra® Ocular Discomfort Scale

• Ora Calibra® Ocular Discomfort & 4-Symptom Questionnaire

• VAS

• BCVA

• Slit lamp biomicroscopy

• Ora Calibra® Conjunctival redness

• Corneal sensitivity (Cochet-Bonnet)

• TFBUT

• Corneal and conjunctival fluorescein staining

• Corneal and conjunctival lissamine green staining

• Unanesthetized Schirmer's Test

• Dispense study drug

• Dispense dosing diary

• Adverse Event Query

	

• Schedule Visit 4

	↓

Visit 4 Day 15 ± 1 day 2-Week Follow-Up
	

• Study Drug Collection

• Medical/medication update

• Adverse event query

• OSDI

• Ora Calibra® Ocular Discomfort Scale

• Ora Calibra® Ocular Discomfort & 4-Symptom Questionnaire

• VAS

• BCVA

• Slit lamp biomicroscopy

• Ora Calibra® Conjunctival redness

• Corneal Sensitivity (Cochet-Bonnet)

• TFBUT

• Corneal and conjunctival fluorescein staining

• Corneal and conjunctival lissamine green staining

• Unanesthetized Schirmer's Test

• Dispense study drug

• Dispense dosing diary

• Adverse Event Query

• Schedule Visit 5

	↓

Visit 5 Day 29 ± 2 days 4-Week Follow-Up and Study Exit
	

• Study drug and diary collection

• Medical/medication update

• Adverse event query

• Urine Pregnancy Test (if applicable)

• OSDI

• Ora Calibra® Ocular Discomfort Scale

• Ora Calibra® Ocular Discomfort & 4-Symptom Questionnaire

• VAS

	

• BCVA

• Slit lamp biomicroscopy

• Ora Calibra® Conjunctival redness

• Corneal sensitivity Cochet-Bonnet

• Tear Osmolarity

• InflammaDry® (MMP-9) testing

• Tear film break-up time (TFBUT)

• Corneal and conjunctival fluorescein staining

• Corneal and conjunctival lissamine green staining

• Unanesthetized Schirmer's Test

• Intraocular Pressure (IOP)

• Dilated fundoscopy

• Blood Draw (optional) for enkephalin testing

• Adverse Event Query

• Study exit

--	--

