## 5.5 Withdrawal Criteria (if applicable)

If at any time during the study the investigator determines that a subject's safety has been compromised, the subject may be withdrawn from the study in particular:

- the occurrence of an exclusion criterion which is clinically relevant and affects the subject's safety, if discontinuation is considered necessary by the investigator.
- the occurrence of an AE if discontinuation of trial drug is desired or considered necessary by the investigator and/or the subject.
- the occurrence of pregnancy.

Subjects may withdraw consent from the study at any time without reason.

The investigator may discontinue any subject for non-compliance or any valid medical reason (see Section 8.6).

The PI and Ora will regularly review the progress of the trial (semi-monthly) including a review of all adverse events noted during the period. In the event of a serious adverse event, the PI shall notify Ora (within 24 hours). Ora and PI will jointly determine whether any amendments to the trial are necessary or if the trial should be discontinued.

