### 8.6.2 Discontinued Subjects

Subjects may be discontinued prior to their completion of the study due to:

- subject request/withdrawal
- AEs
- protocol violations
- administrative reasons (e.g., inability to continue, lost to follow up)
- sponsor termination of study
- other

Note: In addition, any subject may be discontinued for any sound medical reason.

Notification of a subject discontinuation and the reason for discontinuation will be made to Ora and will be clearly documented on the CRF.

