### **9.4 Procedures for Unmasking (if applicable)**

All subjects, investigators, and study personnel involved with the conduct of the study will be masked with regard to treatment assignments. When medically necessary, the investigator may need to determine what treatment arm has been assigned to a subject. When possible (i.e., in non-emergent situations), Ora should be notified before unmasking study drug. Ora must be informed immediately about any unmasking event.

If the investigator identifies a medical need for unmasking the treatment assignment of a subject, he should contact Ora prior to unmasking the identity of the IP, if possible. Ora will ask the site to complete and send them the Unmasking Request Form. Ora will

determine if the unmasking request should be granted. The result of the request will be documented on the Unmasking Request Form. If approval is granted to unmask a subject, written permission via the Unmasking Request Form will be provided to the investigator. The investigator will unmask the subject using the unmasking report. The investigator will complete the Unmasking Memo form and include it in the subject's study file and provide a copy for the Trial Master File (TMF). For each unmasked request, the reason, date, signature, and name of the person who unmasked the subject, must be noted in the subject's study file. Unmasked subjects will be discontinued from the study.

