## **10 STATISTICAL HYPOTHESES AND METHODS OF ANALYSES**

### **10.1 Analysis Populations**

#### Analysis Populations

- Modified Intent-to-Treat Population – The modified intent-to-treat (mITT) population includes all randomized subjects with at least one post visit 2 study assessment. Efficacy analysis will be performed on the mITT population. Subjects in the mITT population will be analyzed as randomized.
- Safety Population – The safety population includes all subjects who have received at least one dose of the investigational product. Subjects in the Safety population will be analyzed as treated.

The statistical analysis of safety data will be performed for the safety population. The analysis of baseline and all efficacy data will be performed for the mITT population.

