### 10.4.3 Missing Data

The efficacy analyses will be performed using observed data.

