## 13 APPENDICES

### APPENDIX 1: SCHEDULE OF VISITS AND MEASUREMENTS

Procedure	Visit 1 Day-10 ±1	Visit 2 Day 1	Visit 3 Day 8 ± 1	Visit 4 Day 15 ± 1	Visit 5 Day 29 ±2
Informed Consent	X				
Demographic Data	X				
Medical/Medication History	X				
Medical/Medication History Update		X	X	X	X
Randomization		X			
Urine pregnancy test	X				X
OSDI ® questionnaire	X	X	X	X	X
Ora Calibra ® Ocular Discomfort Scale	X	X	X	X	X
Ora Calibra ® Ocular Discomfort & 4 Symptom Questionnaire	X	X	X	X	X
Visual Acuity Scale (VAS)	X	X	X	X	X
BCVA	X	X	X	X	X
Slit lamp biomicroscopy	X	X	X	X	X
Ora Calibra ® Conjunctival redness	X	X	X	X	X
Corneal Sensitivity (Cochet-Bonnet)	X	X	X	X	X
Tear Osmolarity		X			X
InflammaDry ® (MMP-9) testing		X			X
TFBUT	X	X	X	X	X

Corneal and conjunctival fluorescein staining	X	X	X	X	X
Corneal and conjunctival lissamine green staining	X	X	X	X	X
Schirmer's Test		X	X	X	X
IOP		X			X
Dilated Fundoscopy		X			X
ENK blood draw (optional)					X
Review Eligibility Criteria	X	X	X	X	X
Run-in (vehicle) instillation at study site	X				
Study drug/placebo instillation at study site		X	X	X	X
Run-in (vehicle) Dispensed	X				
Run-in (vehicle) Returned		X			
Adverse Event Query	X	X	X	X	X
Investigational Product Dispensed		X	X	X	
Investigational Product Returned			X	X	X
Dosing Diary Dispensed	X	X	X	X	
Exit from Study					X

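### Efficacy outcomes after early exit, including Week 4, are not collected, so the observed-data comparison at Visit 5 can be biased if loss is related to outcome

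*Combined protocol and SAP*

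**What the plan says.** Section 4 sets the exit procedure for early leavers: "Participants who terminate early during the application period will be asked to complete safety assessments (if the participants agree) prior to study exit". It adds: "Participants who are terminated early from the study will not be replaced". The visit schedule in Appendix 1 has no early-termination column, although exclusion criterion s in Section 5.4 refers to such a visit for the pregnancy test.

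Two further rules end participation, not only treatment. Section 9.4 states: "Unmasked subjects will be discontinued from the study". Section 5.5 lists among its reasons for withdrawal from the study "the occurrence of an AE if discontinuation of trial drug is desired or considered necessary by the investigator and/or the subject".

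On analysis, Section 10.4.3 consists of one sentence: "The efficacy analyses will be performed using observed data". Section 10.4.6 specifies two-sample t-tests at each visit and on change from baseline, with a Wilcoxon test and a baseline-adjusted ANCOVA as options. No imputation, longitudinal model or missing-data sensitivity analysis is stated. Section 10.4.5 allows an optional per-protocol analysis, but Section 10.1 does not define that population. The mITT "population includes all randomized subjects with at least one post visit 2 study assessment"; the assessment need not be an efficacy assessment.

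**The concern.** Measurement of efficacy stops when the subject exits, and the analysis then uses whoever is still present. Subjects may leave because of an adverse event, lack of benefit or unmasking for medical need, and any of these can be related to treatment and to outcome. The subjects observed at Visit 5 may then no longer represent the groups as randomized.

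Two consequences are specific to this plan. Tear osmolarity has Visit 5 as its only post-baseline time point, so anyone who leaves earlier has no change score. The same holds for MMP-9 under Appendix 1 and Section 8.3.1; the InflammaDry text in Appendix 2 names Visits 1, 3 and 5 instead, and these places need reconciling. Also, a subject who leaves before Visit 3 with only a safety assessment enters the mITT but contributes nothing to any efficacy test.

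The estimates matter despite the exploratory label. Section 10.3 says the efficacy data are meant to help power later trials, so a distorted effect would carry into the next sample size.

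**Working it through.** **The plan's own figures.** There is no planned effect, SD, alpha or dropout rate for efficacy. The one stated probability, 79% for detecting adverse events at a 5% rate, reproduces with 30 subjects in one arm (1 − 0.95^30 = 78.5%). It does not bear on this point. From the documents I take only 30 per arm and the visit structure; everything else below is assumed.

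**Closed form.** Let d be the share of an arm missing at Visit 5, and λ how much worse, in SD, the missing subjects are than those observed. The full mean is (observed mean) − dλ, so the observed-data difference in favour of naltrexone is biased by

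bias = d_A λ_A − d_P λ_P,

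with SE = √(1/n_A + 1/n_P) and n = 30(1 − d). The last column is the two-sided error rate at a nominal 5% (assumed), by normal approximation.

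| Missing, naltrexone / placebo | λ, naltrexone / placebo | Bias (SD) | SE (SD) | Error rate |
|---|---|---|---|---|
| 10% / 10% | 1 / 1 | 0.00 | 0.272 | 5.0% |
| 10% / 10% | 1 / 0 | 0.10 | 0.272 | 6.6% |
| 15% / 5% | 1 / 1 | 0.10 | 0.273 | 6.6% |
| 20% / 5% | 1 / 1 | 0.15 | 0.277 | 8.4% |
| 20% / 5% | 1 / 0 | 0.20 | 0.277 | about 11% |

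Last row: 0.20 × 1 − 0.05 × 0 = 0.20; n = 24 and 28.5; √(1/24 + 1/28.5) = 0.277. Exchanging the arms reverses the sign of the bias.

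**Simulation.** Assumptions: 30 per arm; change scores at Visits 3, 4 and 5 with correlations 0.6–0.7; true effects 0.25, 0.40 and 0.50 SD; loss after Visit 4, logistic in the Visit 4 score with slope 1.5, so that subjects doing badly leave more often.

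| Loss pattern | Loss per arm | Mean observed-data effect at Visit 5 | Shortfall |
|---|---|---|---|
| Random in both arms | any | 0.50 SD | none |
| Same outcome-related rule in both arms | about 6–15% | 0.47 (lower losses) to 0.46 SD (higher losses) | 0.03/0.50 = 6% to 0.04/0.50 = 8% |
| Outcome-related in placebo, random in naltrexone | 9–10% | 0.422 SD | 0.078/0.50 = 16% |
| Outcome-related in placebo, random in naltrexone | 14–15% | 0.384 SD | 0.116/0.50 = 23% |

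In the two placebo-only settings (6,000 trials each), a likelihood-based regression using the Visit 3 and 4 scores gave 0.499 and 0.497 SD, and measuring every leaver at Visit 5 gave 0.499 and 0.496 SD.

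**Limits.** The longitudinal model recovers 0.50 because loss was made to depend only on an observed score (missing at random). Full measurement uses each leaver's true Visit 5 value, whereas an exit assessment is taken on the day of leaving and only approximates it. Unmasking was not simulated.

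**The case against.** The strongest case on the other side has five parts.

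- **Efficacy before exit is measured.** A reader might infer that early leavers have no efficacy outcome at all. The documents do not support that. Section 8.3.1 schedules OSDI, both Ora symptom scales, VAS, redness, corneal sensitivity, TFBUT, both stainings and Schirmer at Visits 3 and 4, and leavers contribute to the tests at every visit they attended. Corneal sensitivity is also listed as a safety endpoint in Section 10.4.5, so it may be taken at exit. Section 8.4.2 lets the investigator add assessments at an unscheduled visit, but does not require them. This stands, and it limits the loss to visits after exit.
- **Improvers are not removed.** Appendix 1 marks "Review Eligibility Criteria" at Visits 3–5, and Section 8.6.2 lists "protocol violations" as a reason for discontinuation. A reader might infer that a subject whose staining falls below 2 becomes ineligible. Inclusion criterion f is tied to Visits 1 and 2, and no text removes a subject for improving. The marks are only a mismatch with Section 8.3.1, which has the review at Visits 1 and 2.
- **The larger biases need an asymmetric pattern.** The 16–23% shortfall arises only when outcome-related loss is confined to placebo. All the biases shown are smaller than the SE of √(2/30) = 0.26 SD with 30 per arm. Both statements are correct. Bias, unlike sampling error, is not reflected in the confidence interval.
- **The study is exploratory and a SAP is to follow.** It has four weeks of treatment and is declared unpowered for efficacy, which lowers the weight of the point. Section 10.4.6 promises a full SAP before lock. A SAP can supply a better model, but it cannot recover assessments that were never made.
- **Unmasked data have a cost.** Many scores are subjective, so data after unmasking may carry reporting bias. Section 9.4 ties unmasking to medical need, and no frequency is given. This makes unmasking a secondary matter.

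**Conclusion.** The concern holds in a limited form. Efficacy outcomes after exit, including Week 4, are not provided for, and t-tests on observed data make no use of a leaver's Visit 3 and 4 scores at Visit 5. The Visit 5 comparison is therefore open to bias if loss is related to outcome; it is not shown to be biased.

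Its size cannot be fixed from the documents. For a true effect of 0.50 SD and assumed Visit 4-driven loss of about 6–15% per arm, the average estimate is 0.46–0.47 SD under a common loss rule and 0.38–0.42 SD if the rule acts in placebo only. The bias is zero under random loss and can take the opposite sign. In an exploratory trial this does not undermine the design, but it is worth correcting because the remedy is cheap and the missing assessments cannot be made later.

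**What to change.** **Section 4 (and an early-termination column in Appendix 1).** At early termination, ask subjects who agree to complete the efficacy assessments as well as the safety assessments, recorded at the actual study day.

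**Sections 10.4.3 and 10.4.6.** Analyse change from baseline with a baseline-adjusted repeated-measures model over Visits 3–5 using all observed data, and keep the by-visit t-tests as supportive. For tear osmolarity and MMP-9, which Appendix 1 schedules after baseline only at Visit 5, use the exit assessment where there is one.

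**Section 9.4 (secondary).** Where the subject agrees, continue the scheduled assessments after unmasking, flag those data, and add a sensitivity analysis that excludes subjective scores obtained after unmasking. This concerns data collection only and leaves treatment decisions untouched.

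**Reconcile.** Bring the eligibility-review marks in Appendix 1 at Visits 3–5 into line with Section 8.3.1, and the MMP-9 visits in Appendix 2 into line with Appendix 1 and Section 8.3.1.

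**Cost.** Protocol and SAP wording, and some extra assessment time for a few leavers with tests and staff already in place. The model relies on a missing-at-random assumption, which the SAP should state. An exit assessment made well before Day 29 is only a partial substitute for Visit 5.
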